6.8.1.2 Classifications

Severity:

Severity of AE or hypoglycaemia episode will be graded as “Mild”, “Moderate” or “Severe”. For AEs or hypoglycaemia episodes with missing severity, the most severe assessment will be imputed for summary analyses.

Causal relationship to study drug:

Causal relationship of AE or hypoglycaemia episode to study drug will be graded as “Reasonable possibility” or “No reasonable possibility”. Any missing relationship of an AE or a hypoglycaemia episode to study drug will be considered as “Reasonable possibility”, following the worst case principle.

Cardiovascular Events:

AEs will be adjudicated whether the AE is cardiovascular event or not. That information will be recorded in the CRF.

6.8.2 Clinical Laboratory Evaluations

Clinical laboratory parameters to be measured and their units for analysis are shown in the following table.

Table 5 Clinical Laboratory Parameters and Units

Variables		Conventional Units	How to Convert	Units for Analysis
Haematology	Haemoglobin	g/dL	-	g/dL
	Haematocrit	%	-	%
	Red blood cell count	$\times 10^6/\mu\text{L}$	Multiply with 10^2	$\times 10^4/\mu\text{L}$
	White blood cell count	$\times 10^3/\mu\text{L}$	Multiply with 10^2	$\times 10/\mu\text{L}$
	Platelet count	$\times 10^3/\mu\text{L}$	Divide by 10	$\times 10^4/\mu\text{L}$
Blood Chemistry	AST	U/L	-	U/L
	ALT	U/L	-	U/L
	Gamma-glutamyl transferase (GGT)	U/L	-	U/L
	Lactate dehydrogenase (LDH)	U/L	-	U/L
	Alkaline phosphatase	U/L	-	U/L
	Total bilirubin	mg/dL	-	mg/dL
	Total cholesterol	mg/dL	-	mg/dL
	Triglycerides	mg/dL	-	mg/dL

Variables		Conventional Units	How to Convert	Units for Analysis
Blood Chemistry	Low-density lipoprotein cholesterol (LDL-C)	mg/dL	-	mg/dL
	High-density lipoprotein Cholesterol (HDL-C)	mg/dL	-	mg/dL
	Blood urea nitrogen	mg/dL	-	mg/dL
	Creatinine	mg/dL	-	mg/dL
	Uric acid	mg/dL	-	mg/dL
	Total protein	g/dL	-	g/dL
	Albumin	g/dL	-	g/dL
	Globulin	g/dL	-	g/dL
	Albumin/globulin ratio	-	-	-
	Direct bilirubin	mg/dL	-	mg/dL
	Creatine kinase	U/L		U/L
	Sodium	mEq/L	-	mEq/L
	Potassium	mEq/L	-	mEq/L
	Chloride	mEq/L	-	mEq/L
	Calcium	mg/dL	-	mg/dL
	Magnesium	mg/dL	-	mg/dL
	Phosphate	mg/dL	-	mg/dL
Urinalysis	Glucose	-	-	-
	Protein	-	-	-
	Occult blood	-	-	-
	Urobilinogen	-	-	-
	Ketone bodies	-	-	-
	pH	-	-	-

Any value "Lower Limit of Quantification", e.g. "< x.xx" will be analysed as numerical value "x.xx".

Females of childbearing potential will have serum pregnancy test.

6.8.3 Vital Signs

Vital signs assessment includes measurement of systolic and diastolic blood pressure (mmHg), pulse rate (beats/min), body temperature (celcius) and height (cm).

6.8.4 Electrocardiogram (ECG)

Standard 12- Lead ECG will include recording PR-interval (ms), RR-interval (ms), QRS-interval (ms), QT-interval (ms), QTc (ms) and heart rate (beats/min).

ECGs will be assessed by the Investigators and graded as:

- normal
- abnormal, not clinically significant
- abnormal, clinically significant

6.8.5 Physical Examination

This evaluation will include an examination of general appearance, head, eyes, ears, nose and throat, skin, neck, lungs, cardiovascular, breast, lymph nodes, abdomen, musculoskeletal, neurological and other. These examinations will be categorized as normal or abnormal by the investigator.

7 STATISTICAL METHODS

7.1 General Methodology

All analyses will be performed after the database is locked and access has been removed from the database and the study treatment codes are unblinded.

All statistical tests will be two-sided with a significance level of $\alpha=0.05$, unless specified otherwise and will be performed using SAS® Version 9.2 or higher.

Statistical tests will be supported by presenting estimates and 95% confidence intervals (CI) for the respective treatment effects and differences between the treatment groups. These estimates, confidence intervals and p-value will be based on the respective statistical models used for the analysis.

Data will be summarized using descriptive statistics (number of non-missing values [n], mean, standard deviation [SD], median, minimum, and maximum) for continuous variables and using frequency counts and percentage for discrete variables.

For the purpose of display, the summary results will be rounded as follows:

- Min and Max: same number of decimals as the raw data.
- Mean and Median: one more decimal place than the raw data.
- SD/Standard Error (SE): one more decimal places than the raw data.
- Percentages will be displayed with one decimal precision. A zero count will not have the associated percentage presented on the table (i.e. no 0%).
- All p-values will be displayed with a leading zero except when the value is 1. All p-values will be displayed to four decimal places. If a p-value is less than 0.0001, then the value will be displayed as '<0.0001'. If a p-value is 1, then the value will be displayed as 1.0000. If the p-value cannot be calculated for any reason, the value listed will be 'NA'.
- CI: one more decimal place than the raw data.

For categorical variables with missing values, a category documenting the frequency of missing values will be displayed in the summary tables.

Subject listings of all data from the CRFs as well as any derived variables will be presented. Safety listings of clinical laboratory, vital signs and ECG will be presented by planned visit.

7.2 Adjustments for Covariates

The efficacy variable being analysed will be adjusted for its baseline value, as a covariate in the model.

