Once a suitable candidate is identified from among the outpatients coming to the site for the scheduled visit, the investigator or designated healthcare professional will ask the subject about their willingness to be included in the clinical trial. The subject is to be informed verbally and in writing about the nature, risks, benefits, and expectations of participating in the clinical trial and a copy of the subject informed consent form is to be given to the subject in the appropriate language. The subject informed consent form is to be signed by the subject and countersigned by the attending investigator prior to proceeding with the visit. At this point, a subject screening number is to be assigned.

The investigator will provide subjects with a subject diary and glucometer, and will instruct them when and how to write in the subject diary and also when and how to monitor their own blood glucose by glucometer. The subjects should write in the subject diary and should monitor their blood glucose by glucometer as much as possible when hypoglycaemia occurs. The subjects should visit the investigator promptly when the hypoglycaemia is not recovered by the treatment such as taking glucose.

The following observations/procedures are to be performed and checked:

- Check inclusion/exclusion criteria
- Obtain written informed consent
- Complete physical examination including body weight, height, vital signs and ECG
- Complete demographic data and medical history
- Review use of previous/concomitant treatments and of the regular metformin therapy
- Conduct a pregnancy test for female subjects of childbearing potential at the screening visit. Female subjects of childbearing potential have to confirm that they are using approved means of contraception. Menopause and hysterectomy and/or oophorectomy are to be documented.
- Blood and urine is to be drawn and sent to the central laboratory according to the local procedure for evaluation of haematology, clinical chemistry, urinalysis, HbA1c, and FPG.
- Subjects will be instructed to return for the placebo run-in visit 2 weeks later.
- Dispense of subject diary and glucometer.

Placebo Run-in Visit (14 days plus/minus 3 days prior to treatment)

The following observations/procedures are to be performed and checked:

- Check inclusion/exclusion criteria
- Review of subject's clinical charts, results of laboratory examination and blood pressure to confirm entry criteria
- Vital signs

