- Blood is to be drawn and sent to the central laboratory* according to the local procedure for evaluation of HbA1c, and FPG.
- Evaluation for any AEs including hypoglycaemic episodes experienced by the subjects since last visit
- Subjects receive single-blinded placebo to take once daily. This will be dispensed to the subjects. Subjects should start administration of placebo from the placebo run-in visit.
- Review of subject diary
- Subjects are to be instructed that they have to return for the next scheduled visit day.

* When the investigator considers there are proper reasons, it is allowed to evaluate HbA1c and FPG at each study site.

Randomization Visit (1 day of treatment)

The following observations/procedures are to be performed and checked:

- Check inclusion/exclusion criteria
- Review of subject's clinical charts, results of laboratory examination and blood pressure to confirm entry criteria
- Vital signs, body weight and ECG
- Review use of concomitant treatments and of the regular metformin therapy
- Blood and urine is to be drawn and sent to the central laboratory according to the local procedure for evaluation of haematology, clinical chemistry, urinalysis, HbA1c, FPG, fasting insulin, C-peptide and glucagon
- Evaluation for any AEs including hypoglycaemic episodes experienced by the subjects since last visit
- Review subject diary

- Randomization to MP-513 or placebo. This will be dispensed to the subjects. Unused placebo from the placebo run-in period has to be returned to the site. Investigator calculates the drug compliance of the placebo run-in period and confirms whether the subject doesn't meet the exclusion criteria #18. Subjects should start administration of MP-513 or placebo from the randomization visit.
- Subjects are to be instructed that they have to return for the next scheduled visit day.

Treatment Visit 1 (Week 4 plus/minus 7 days of treatment)

The following observations/procedures are to be performed and checked:

- Vital signs, body weight
- Review use of concomitant treatments and of the regular metformin therapy
- Blood and urine is to be drawn and sent to the central laboratory according to the local procedure for evaluation of haematology, clinical chemistry, urinalysis, HbA1c, FPG, fasting insulin, C-peptide and glucagon
- Evaluation for any AEs including hypoglycaemic episodes experienced by the subjects since last visit
- Review subject diary

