6.3 Baseline Assessments

Baseline assessments will be the most recent assessment prior to the randomization.

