8.7.1 Analysis of Primary Efficacy Variable

8.7.1.1 Primary Analysis of Primary Efficacy Variable

The primary efficacy endpoint is to evaluate the change in HbA1c from baseline to Week 24 in the group receiving MP-513 compared with the group receiving placebo in Chinese subjects with

type 2 diabetes mellitus inadequately controlled with metformin accompanying with diet and exercise. The reduction in HbA1c value indicates improvement.

The primary efficacy will be assessed by testing the null hypothesis that, there is no difference in the change in HbA1c from baseline to Week 24 in the group receiving MP-513 compared to the group receiving Placebo. In statistical notation the hypothesis is defined as follows:

Null Hypothesis $H_0: \mu_{MP-513} = \mu_{Placebo}$

Alternate Hypothesis $H_A: \mu_{MP-513} \neq \mu_{Placebo}$

Where μ_{MP-513} : Mean change in HbA1c from baseline at week 24 for MP-513

$\mu_{Placebo}$: Mean change in HbA1c from baseline at week 24 for placebo

The missing HbA1c values at week 24 will be imputed using LOCF approach prior to analysis. The change in HbA1c from baseline to Week 24 (LOCF) will be analysed using analysis of covariance (ANCOVA) with treatment as a fixed effect and baseline value as a covariate in the model.

For the treatment effects and the difference between the treatment groups, the least square means from ANCOVA will be presented along with the corresponding SE and CI. The treatment difference in mean change from baseline will be computed using the model. The p-values for the test of significance, SE and CI of the mean difference will be presented.

The change in HbA1c from baseline for all the post baseline assessments visits, Week 12 (LOCF) and Week 24 (LOCF) will also be summarized as continuous variable using descriptive statistics.

The line graph for mean change in HbA1c from baseline to Week 24 and Week 24 (LOCF) will be presented. The 95% CIs will also be shown in the graph with error bar. The plots of Week 24 and Week 24 (LOCF) will not be connected.

8.7.1.2 *Supportive Analysis of Primary Efficacy Variable*

The study will have two supportive analyses to be performed on primary efficacy variable i.e. change in HbA1c from baseline to Week 24, as follows:

- The change in HbA1c from baseline to Week 24 in MP-513 compared to Placebo will be performed on PPS using the same statistical methodology as described for the primary analysis.

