8.7.2 Analysis of Secondary Efficacy Variables

All analysis on secondary efficacy variables will be performed using FAS.

The secondary efficacy endpoint is to evaluate the change in FPG from baseline to week 24 of MP-513 compared to Placebo. The same statistical methodology as described for primary analysis on primary efficacy endpoint will be used.

The line graph for mean change in FPG from baseline to Week 24 and Week 24 (LOCF) will be presented. The 95% CIs will also be shown in the graph with error bar. The plots of Week 24 and Week 24 (LOCF) will not be connected.

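### The FPG and HbA1c models adjust only for the last pre-randomisation value and leave the Day -28 and Day -14 readings unused; the analysis is valid but gives up some precision, mainly for FPG

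*SAP*

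**What the plan says.** SAP 7.2 sets one rule for all efficacy models: "The efficacy variable being analysed will be adjusted for its baseline value, as a covariate in the model". SAP 6.3 defines that value: "Baseline assessments will be the most recent assessment prior to the randomization". In the visit schedule this is normally the Day 1 sample.

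SAP 8.7.1.1 analyses HbA1c by "analysis of covariance (ANCOVA) with treatment as a fixed effect and baseline value as a covariate in the model". For FPG, the only secondary endpoint, SAP 8.7.2 says: "The same statistical methodology as described for primary analysis on primary efficacy endpoint will be used". The supportive MMRM (SAP 8.7.1.2) and the code in SAP 11.1.1 and 11.1.2 also carry the single term `base`. Protocol 6.9.1.5 agrees.

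Protocol 6.6.1 collects both variables twice more before randomisation. At screening (Day -28), samples go to the central laboratory "for evaluation of haematology, clinical chemistry, urinalysis, HbA1c, and FPG". At the run-in visit (Day -14): "Blood is to be drawn and sent to the central laboratory* according to the local procedure for evaluation of HbA1c, and FPG". A footnote there lets a site measure the Day -14 values itself if the investigator sees proper reasons. Inclusion criteria 6 and 7 (Protocol 6.3.1) apply HbA1c and FPG limits at both visits.

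**The concern.** A single fasting glucose varies from day to day, so one reading is a noisy measure of a subject's usual level. Each randomised subject should have two further readings, taken on metformin, diet and exercise that were to be unchanged from at least 8 weeks before screening. Where Day 1 differs from the usual level through short-term variation, those readings help predict Week 24 and reduce residual variance.

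The plan itself allows for such variation. Entry requires HbA1c of at least 7.0% on Day -28 and Day -14, yet SAP 7.10 defines a subgroup with baseline below 7.0%, and SAP 8.7.3 excludes such subjects from the responder model.

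At stake is the width of the confidence intervals, chiefly for FPG. All three readings precede double-blind dosing, so a prespecified covariate built from them does not bias the randomised comparison.

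**Working it through.** **The plan's own figure.** SAP 4.5 gives 86 per group for a 0.5% difference, SD 1.0%, two-sided 0.05 and 90% power. The noncentral t gives power 0.903 at 86 and 0.8999 at 85, so 86 reproduces. For 30% drop-out, 86/0.7 = 123 and 86 × 1.3 = 112; the planned 120 lies between. The calculation is a two-sample t-test and takes no credit for any covariate.

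**Inputs.** The documents give no within-subject variance or correlation for either variable, and no FPG SD. All SDs below are assumptions.

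| | between-subject b | within-subject w | true change c |
|---|---|---|---|
| FPG, mg/dL | 25-35 | 12-20 | 15-25 |
| HbA1c, % | 0.60-0.75 | 0.15-0.25 | 0.5-0.9 |

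**Step 1: exchangeable readings.** With k baseline readings,

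V(k) = b²[1 − b²/(b² + w²/k)] + c² + w².

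Comparing k = 1 with k = 3:

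- FPG, smallest (25, 12, 25): 886.0 to 813.6, a cut of 8.2%.
- FPG, largest (35, 20, 15): 926.5 to 745.2, a cut of 19.6%.
- HbA1c, smallest (0.60, 0.15, 0.9): 0.8537 to 0.8398, a cut of 1.6%.
- HbA1c, largest (0.75, 0.25, 0.5): 0.3687 to 0.3326, a cut of 9.8%.

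The last case implies an SD of change of √(c² + 2w²) = √(0.25 + 0.125) = 0.61%, well below the SAP's 1.0%. Holding the SD of change at 1.0%, the HbA1c cut is 1.4-3.6%. At 0.75%, the SD in the earlier Japanese biguanide-combination group (Protocol section 4), it is 2.5-6.5%.

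**Step 2: drift.** Let the true level have autocorrelation φ = 0.95 to 0.98 per week (assumed), and put p = φ² for each two-week gap. Let m be the mean of the Day -28 and Day -14 readings, and x the Day 1 reading. Then

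- C = Cov(true Day 1 level, m) = b²(p + p²)/2
- Var(m) = b²(1 + p)/2 + w²/2
- Var(x) = b² + w²
- variance removed by adding m = [C·w²/Var(x)]² / [Var(m) − C²/Var(x)].

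FPG, low end (35, 12, 25; φ = 0.95): C = 1051.7, Var(m) = 1237.3, Var(x) = 1369. Removed: 110.6²/429.4 = 28.5. With Day 1 alone the residual is 897.9, so the cut is 3.2%.

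FPG, high end (35, 20, 15; φ = 0.98): C = 1153.2, Var(m) = 1400.7, Var(x) = 1625. Removed: 283.9²/582.3 = 138.4. Cut: 138.4/926.5 = 14.9%.

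HbA1c, low end (0.75, 0.15, 0.9; φ = 0.95): removed 0.01857²/0.1477 = 0.0023. Cut: 0.0023/0.8541 = 0.3%.

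HbA1c, high end (0.60, 0.25, 0.5; φ = 0.98): removed 0.05013²/0.1123 = 0.0224. Cut: 0.0224/0.3658 = 6.1%.

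Simulating the eligibility limits on Day -28 and Day -14 moves these ends only slightly. The ranges are therefore roughly 3-15% for FPG and 0-6% for HbA1c.

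**Step 3: a second parametrisation.** Let ρ be the correlation among pre-treatment readings and r their correlation with Week 24. Compare 1 − r² with 1 − 3r²/(1 + 2ρ). This, together with simulations that apply the eligibility limits, multiplies FPG residual variance by 0.86-0.93 and HbA1c residual variance by 0.95-0.99. If the readings follow a Markov drift with no measurement error, the gain is zero.

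**Step 4: cost.** One degree of freedom costs 1/(240 − 4) = 0.4% of variance with all 240 subjects, or 1/(172 − 4) = 0.6% with 86 per group. For HbA1c with ρ of 0.95-0.98 and r = 0.3, the net variance ratio is 1.001-1.003, which is no gain.

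**Step 5: what it is worth.** For FPG, 240/0.97 = 247 and 240/0.85 = 282, so the gain equals about 7 to 42 extra subjects. The standard error falls by 1 − √0.97 = 1.5% to 1 − √0.85 = 7.8%. For HbA1c at 86 per group, taking 1.0% as the residual SD, power moves from 90.3% to 90.6% (variance × 0.99) or 91.7% (× 0.95).

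**The case against.** The strongest reply is that nothing here is an error. ANCOVA on the last pre-randomisation value is standard and valid, and protocol and SAP state it consistently. That stands. A reader might infer that the primary analysis is biased or the trial underpowered; the documents support neither, because the 86 per group takes no credit for covariates and FPG has no power target to miss.

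The older readings may also add less than exchangeability suggests. Placebo starts at the Day -14 visit, so both readings precede the run-in, and eligibility truncates both but not Day 1. A shift common to all subjects is absorbed by the model. Decaying correlation and truncation do reduce the gain, which is why the 3-15% range is used for FPG and the 20% figure is only an upper limit.

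A reader might go further and say that the change sharpens both estimates, with the same assay, at no cost. Each part is too strong:

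- For HbA1c the gain may be nil.
- The same assay is not guaranteed, since Day -14 may be measured locally. In a simulation with 20% local values (assumed bias 0.2, SD 0.3), the HbA1c variance ratio was 0.978 against 0.975 without, so the harm is small.
- There is a cost: one degree of freedom, and a rule for a subject with no Day 1 value. Under SAP 6.3 that subject's baseline is the Day -14 reading, which would otherwise enter the model twice.

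**Conclusion.** The point holds as an efficiency suggestion, mainly for FPG. Readings that the protocol already requires go unused in every FPG and HbA1c model. Using them would probably cut FPG residual variance by about 3-15%, and by up to about 20% only if the three readings are exchangeable. For HbA1c the cut is about 0-6%, possibly nothing after the lost degree of freedom. These ranges rest on assumed variance components and drift, and the documents can neither confirm nor narrow them. Validity, type I error and the planned power are not in question. Lowest severity: a cheap improvement.

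**What to change.** Before unblinding, revise SAP 7.2, 8.7.2 and 11.1.1. Keep the baseline value and add one covariate to the FPG ANCOVA: the mean of the central-laboratory Day -28 and Day -14 values. Use Day -28 alone when the Day -14 value was measured locally, is missing, or is itself the baseline.

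The same term may be prespecified for the HbA1c ANCOVA and MMRM (SAP 8.7.1.1, 8.7.1.2 and 11.1.2), without expecting much from it.

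SAP 8.7.2 now simply borrows the primary method, so the FPG model needs its own sentence. Protocol 6.9.1.5 names baseline as the only covariate, so the addition should be recorded in SAP section 5 as a change to the planned analysis.

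Cost: one degree of freedom (about 0.4-0.6% of variance), one model term and one fallback sentence. No new visit, sample or subject is needed.

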7.3 Handling of Dropouts or Missing Data

Subjects who discontinue the study prior to or after the initiation of the study drug will not be replaced and available data of these subjects until the point of discontinuation will be summarized. The missing baseline assessment will not be imputed.

For categorical variables with missing values, a category documenting the frequency of missing values will be displayed in the summary tables.

The missing HbA1c and FPG value at week 12 or week 24 will be imputed using last observation carried forward (LOCF) approach. Baseline value will not be used to impute missing data. The missing data of Fasting insulin, C-peptide, Glucagon, HOMA-IR, HOMA- β and Body weight at week 24 will also be imputed using LOCF approach.

The supportive analysis for primary efficacy will be done using observed values.

There will be no imputation of missing values in database of safety data, however missing relationship between AE and study medication will be considered as related to treatment following worst case principle. Missing severity of an AE will be summarized as severe AE.

7.3.1 TEAE status when start date is unknown

The following rules will apply in cases where start date of an AE is unknown:

- If the AE onset date is unknown and the end date is after Day 1 or ongoing, then the AE will be considered a TEAE.
- If the AE onset date is unknown and the end date is before Day 1, then the AE will not be considered a TEAE.
- If both the start and end dates are unknown (or end date is ongoing), then the AE will be considered a TEAE, following the worst case principle.

The same rule will be applied in cases where start date of a hypoglycemic episode is unknown.

